### **Financial Disclosure**

Investigators and sub-Investigators will provide the Sponsor or designee [CCI] with sufficient, accurate financial information as requested to allow the Sponsor or designee [CCI] to submit complete and accurate financial certification or disclosure statements to the appropriate regulatory authorities. Investigators are responsible for providing information on financial interests during the course of the study and for one year after completion of the study.

### **Insurance**

Sponsor will provide insurance in accordance with local guidelines and requirements as a minimum for the patients in this study. The terms of the insurance will be kept in the study files.

Due to the coronavirus public health crisis, in the US the federal government has a program that may provide compensation to the patient or their family if the patient experiences serious physical injuries or death as a result of participating in this clinical trial covered by the Public Readiness and Emergency Preparedness Act. More information regarding this Countermeasures Injury Compensation Program is available at <https://www.hrsa.gov/cicp/index.html> or by calling [name].

### **Informed Consent Process**

The Investigator or his/her representative will explain the nature of the study to the patient or his/her legally authorized representative and answer all questions regarding the study.

Patients must be informed that their participation is voluntary. Patients or their legally authorized representative will be required to sign a statement of informed consent that meets the requirements of 21 CFR 50, local regulations, ICH guidelines, Health Insurance Portability and Accountability Act requirements, where applicable, and the IRB/IEC or study center.

The medical record must include a statement that informed consent was obtained before the patient was entered in the study and the date the consent was obtained. The authorized person obtaining the informed consent must also sign the ICF.

Patients must be re-consented to the most current version of the ICF(s) during their participation in the study.

A copy of the ICF(s) must be provided to the patient or the patient’s legally authorized representative.

### **Data Protection**

Patients will be assigned a unique identifier by CCI. Any patient records or datasets that are transferred to the Sponsor, designee CCI, or any candidate agent owner will contain the identifier only; patient names or any information which would make the patient identifiable will not be transferred.

The patient must be informed that his/her personal study-related data will be used by the Sponsor in accordance with local data protection law. The level of disclosure must also be explained to the patient.

The patient must be informed that his/her medical records may be examined by Clinical Quality Assurance auditors or other authorized personnel appointed by the Sponsor, by appropriate IRB/IEC members, and by inspectors from regulatory authorities.

### **Administrative Structure**

The trial will be overseen by a JSC that has decision-making rights on critical decisions that impact the platform trial. The JSC, at a minimum, will be composed of a senior representative of each company participating in the trial.

The administrative structure will be documented in more detail in the Trial Master File.

### **Dissemination of Clinical Study Data**

The results of the study should be reported within one year from the end of the overall clinical study. Irrespective of the outcome, the Sponsor will submit to US National Institutes of Health’s website [www.ClinicalTrials.gov](http://www.ClinicalTrials.gov) and other publicly-accessible sites within one year from the end of the overall clinical study. It shall be accompanied by a summary written in a manner that is understandable to laypersons.

## Data Quality Assurance

All patient data relating to the study will be recorded on eCRFs unless transmitted to the Sponsor or designee [CCI] electronically (eg, laboratory data). The Investigator is responsible for verifying that data entries are accurate and correct by physically or electronically signing the eCRF.

The Investigator must maintain accurate documentation (source data) that supports the information entered in the eCRF.

The Investigator must permit study-related monitoring, audits, IRB/IEC review, and regulatory agency inspections and provide direct access to source data documents.

The Sponsor or designee [CCI] is responsible for the data management of this study including quality checking of the data.

Study monitors will perform ongoing source data review to confirm that data entered into the eCRF by authorized study center personnel are accurate, complete, and verifiable from source documents; that the safety and rights of patients are being protected; and that the study is being conducted in accordance with the currently approved protocol and any other study agreements, ICH GCP, and all applicable regulatory requirements.

Records and documents, including signed ICFs, pertaining to the conduct of this study must be retained by the Investigator in accordance with local regulations. No records may be destroyed during the retention period without the written approval of the Sponsor. No records may be transferred to another location or party without written notification to the Sponsor.

## Source Documents

The Investigator/institution should maintain adequate and accurate source documents and study records that include all pertinent observations on each of the study center's patients. Source data should be attributable, legible, contemporaneous, original, accurate, and complete. Changes to source data should be traceable, should not obscure the original entry, and should be explained if necessary (eg, via an audit trail).

Source documents provide evidence for the existence of the patient and substantiate the integrity of the data collected. Source documents are filed at the Investigator's study center.

Data reported on the eCRF or entered in the eCRF that are transcribed from source documents must be consistent with the source documents or the discrepancies must be explained. The Investigator may need to request previous medical records or transfer records, depending on the study. Also, current medical records must be available.

Definition of what constitutes source data can be found in the eCRF completion guidelines.

## **Study and Study Center Closure**

The Sponsor reserves the right to close the study center or terminate the study at any time for any reason at the sole discretion of the Sponsor. Study centers will be closed upon study completion. A study center is considered closed when all required documents and study supplies have been collected and a study center closure visit has been performed.

The Investigator may initiate study center closure at any time, provided there is reasonable cause and sufficient notice is given in advance of the intended termination.

Reasons for the early closure of a study center by the Sponsor or Investigator may include but are not limited to:

- Failure of the Investigator to comply with the protocol, the requirements of the IRB/IEC or local health authorities, the Sponsor's procedures, or GCP guidelines.
- Inadequate recruitment of patients by the Investigator.
- Discontinuation of further study treatment development.

## **Publication Policy**

To coordinate dissemination of data from this study, the Sponsor may facilitate the formation of a Publication Committee, the governance and responsibilities of which are set forth in a Publication Charter. The committee is expected to solicit input and assistance from other Investigators and to collaborate with authors and Amgen staff, as appropriate, as defined in the Publication Charter. Membership on the committee does not guarantee authorship. The criteria described below are to be met for every publication.

Authorship of any publications resulting from this study will be determined on the basis of the Uniform Requirement for Manuscripts Submitted to Biomedical Journals International Committee of Medical Journal Editors Recommendations for the Conduct of Reporting, Editing, and Publications of Scholarly Work in Medical Journals, which states: Authorship credit is to be based on: (1) substantial contributions to conception and design, acquisition of data, or analysis and interpretation of data; (2) drafting the article or revising it critically for important intellectual content; (3) final approval of the version to be published; and (4) agreement to be accountable for all aspects of the work in ensuring that questions related to the accuracy or integrity of any part of the work are appropriately investigated and resolved. Authors need to meet conditions 1, 2, 3, and 4.

When a large, multicenter group has conducted the work, the group is to identify the individuals who accept direct responsibility for the manuscript. These individuals must fully meet the criteria for authorship defined above. Acquisition of funding, collection of data, or general supervision of the research group, alone, does not justify authorship. All persons designated as authors must qualify for authorship, and all those who qualify are to be listed. Each author must have participated sufficiently in the work to take public responsibility for appropriate portions of the

content. All publications (eg, manuscripts, abstracts, oral/slide presentations, book chapters) based on this study must be submitted to the Publication Committee for review. The Clinical Trial Agreement among the institution, Investigator, and the Consortium will detail the procedures for, and timing of, the Publication Committee’s review of publications.

### **Appendix 3            Clinical Laboratory Tests**

The minimum tests to be performed are detailed in [Table 5](#). Any additional tests that are specific for the candidate agent will be detailed in the corresponding sub-protocol. Clinical laboratory tests will be performed at a local laboratory.

Protocol-specific requirements for inclusion or exclusion of patients are detailed in [Section 5.0](#) of the protocol.

Additional tests may be performed at any time during the study as determined necessary by the Investigator or required by local regulations.

Changes to some laboratory parameters are anticipated for any patients moving on to ECMO therapy.

Investigators must document their review of each laboratory safety report.

**Table 5 Protocol-required Safety Laboratory Assessments**

Laboratory Assessments	Parameters
Hematology	Platelet Count Hemoglobin White blood cell count with differential: Neutrophils Lymphocytes Monocytes Eosinophils Basophils
Coagulation	D-dimer test Fibrinogen Activated partial thromboplastin time (aPTT) Prothrombin time (PT) International Normalized Ratio (INR) C-reactive protein Ferritin Lactate dehydrogenase (LDH) Procalcitonin
Clinical Chemistry	Potassium Sodium Calcium Magnesium Phosphate Bicarbonate Creatinine Glucose
Liver Function Tests	Alkaline phosphatase Total bilirubin Aspartate aminotransferase (AST) Alanine aminotransferase (ALT) Gamma-glutamyl transferase (GGT)
Cardiac Panel	Creatine kinase (MB fraction) Triglycerides Troponin

## Appendix 4 Adverse Events: Definitions and Procedures for Recording, Evaluating, Follow-up, and Reporting

For completeness, the full guidance for AE reporting is presented in this appendix.

### Definition of AE

AE Definition

 
• An AE is any untoward medical occurrence in a patient or subject, temporally associated with the use of study treatment, whether or not considered related to the study treatment.
 
• NOTE: An AE can therefore be any unfavorable and unintended sign (including an abnormal laboratory finding), symptom, or disease (new or exacerbated) temporally associated with the use of study treatment.
 

Events Meeting the AE Definition

 
• Any abnormal laboratory test results (hematology, clinical chemistry, or urinalysis) or other safety assessments (eg, ECG, radiological scans, vital signs measurements), including those that worsen from baseline, considered clinically significant in the medical and scientific judgment of the Investigator.
 
• Exacerbation of a chronic or intermittent pre-existing condition including either an increase in frequency and/or intensity of the condition.
 
• New conditions detected or diagnosed after study treatment administration even though it may have been present before the start of the study.
 
• Signs, symptoms, or the clinical sequelae of a suspected drug-drug interaction.
 
• Signs, symptoms, or the clinical sequelae of a suspected overdose of either study treatment or a concomitant medication. Overdose per se will not be reported as an AE/SAE unless it is an intentional overdose taken with possible suicidal/self-harming intent. Such overdoses should be reported regardless of sequelae.
 
• “Lack of efficacy” or “failure of expected pharmacological action” per se will not be reported as an AE or SAE. Such instances will be captured in the efficacy assessments. However, the signs, symptoms, and/or clinical sequelae resulting from lack of efficacy will be reported as AE or SAE if they fulfill the definition of an AE or SAE.
 

Events NOT Meeting the AE Definition

 
• Medical or surgical procedure (eg, endoscopy, appendectomy): the condition that leads to the procedure is the AE.
 
• Situations in which an untoward medical occurrence did not occur (social and/or convenience admission to a hospital).
 
• Anticipated day-to-day fluctuations of pre-existing disease(s) or condition(s) present or detected at the start of the study that do not worsen.
 

## Definition of SAE

If an event is not an AE per definition above, then it cannot be an SAE even if serious conditions are met (eg, hospitalization for signs/symptoms of the disease under study, death due to progression of disease).

An SAE is defined as any untoward medical occurrence that, at any dose:
a) Results in death
b) Is life-threatening The term ‘life-threatening’ in the definition of “serious” refers to an event in which the patient was at risk of death at the time of the event. It does not refer to an event, which hypothetically might have caused death, if it were more severe.
c) Requires inpatient hospitalization or prolongation of existing hospitalization In general, hospitalization signifies that the patient has been detained (usually involving at least an overnight stay) at the hospital or emergency ward for observation and/or treatment that would not have been appropriate in the physician’s office or outpatient setting. Complications that occur during hospitalization are AEs. If a complication prolongs hospitalization or fulfills any other serious criteria, the event is serious. When in doubt as to whether “hospitalization” occurred or was necessary, the AE should be considered serious. Hospitalization for elective treatment of a pre-existing condition that did not worsen from baseline is not considered an AE.
d) Results in persistent disability/incapacity 
 
• The term disability means a substantial disruption of a person’s ability to conduct normal life functions.
 
• This definition is not intended to include experiences of relatively minor medical significance such as uncomplicated headache, nausea, vomiting, diarrhea, influenza, and accidental trauma (eg, sprained ankle) which may interfere with or prevent everyday life functions but do not constitute a substantial disruption.
 

e) Is a congenital anomaly/birth defect
f) Other situations: 
 
• Medical or scientific judgment should be exercised in deciding whether SAE reporting is appropriate in other situations such as important medical events that may not be immediately life-threatening or result in death or hospitalization but may jeopardize the patient or may require medical or surgical intervention to prevent one of the other outcomes listed in the above definition. These events should usually be considered serious. Examples of such events include invasive or malignant cancers, intensive treatment in an emergency room or at home for allergic bronchospasm, blood dyscrasias, or convulsions that do not result in hospitalization, or development of drug dependency or drug abuse.
 

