#### **8.4.7 Disease-Related Events and/or Disease-Related Outcomes**

Progression, signs, or symptoms of the disease being studied and clinically significant abnormal laboratory findings or other abnormal safety assessments which are associated with the underlying disease should be reported, as appropriate, as an AE or SAE.

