17.1. ADVERSE EVENTS

Each AE will be classified as either:

- Prior, defined as any AE that started or worsened in severity on or after the date of signed informed consent but before the first dose of study drug;
- Treatment-emergent, defined as any AE that started or worsened in severity on or after the first dose of study drug.

If time of the first dose of study drug and time of start of AEs are available, then the times will be taken into account for determining TEAEs. Refer to [Appendix 1](#) for handling of partial and completely missing dates for AEs. In the case where it is not possible to define an AE as treatment emergent or not, the AE will be classified by the worst case; i.e. treatment emergent.

AEs will be coded using the MedDRA dictionary, version 23.1 or later. Summaries by System Organ Class and PT will be sorted as follows: System Organ Classes will be sorted in alphabetical order and within each System Organ Class, PTs will be sorted by decreasing order to total frequency.

An overall summary of number and percentage of patients within each of the categories described in the sub-sections below will be provided by treatment arm. Should a patient experience multiple events within a category, the patient will be counted only once for that category. Additionally, the risk difference of the overall incidence rates of serious TEAEs and overall incidence rates of AESIs (when applicable for a sub-protocol) between treatment and control arms will be presented along with its 95% two-sided Wald CI.

[figure not shown]
All AEs (prior and TEAE) will be listed.

CCI

PPD

Version Number: Amendment 1, v1.0
Version Date: 23Apr2021

CCI

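### Master Protocol Appendix 4 gives COVID-19 progression deaths and disease hospitalizations as examples of events that cannot be SAEs, against Section 8.4.7, so sites can record them differently

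*Protocol*

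**What the plan says.** Master Protocol Appendix 4, Definition of SAE, opens with a condition: "If an event is not an AE per definition above, then it cannot be an SAE even if serious conditions are met". The examples that follow in parentheses are "hospitalization for signs/symptoms of the disease under study, death due to progression of disease". No other example is given.

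Section 8.4.7, the section devoted to disease-related events and outcomes, takes as its subject "Progression, signs, or symptoms of the disease being studied", together with clinically significant abnormal laboratory or other safety findings associated with the disease. Its instruction is that these "should be reported, as appropriate, as an AE or SAE".

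Appendix 4, Definition of AE, includes any unfavorable "symptom, or disease (new or exacerbated) temporally associated with the use of study treatment". In the list of events that are not AEs, the only item about the course of a disease is "Anticipated day-to-day fluctuations of pre-existing disease(s) or condition(s) present or detected at the start of the study that do not worsen".

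Master SAP 17.1.2 and 17.1.3 identify fatal TEAEs and SAEs from the Adverse Events page of the eCRF. Section 17.1 adds "the risk difference of the overall incidence rates of serious TEAEs" between treatment and control arms, with a 95% Wald CI.

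**The concern.** The patients are hospitalized at Grade 2 to 5 on the ordinal scale, some of them on ventilation or ECMO, so serious worsening of COVID-19 is an expected kind of event. For that kind of event a site can cite Appendix 4 for leaving it off the Adverse Events page, or Section 8.4.7 for entering it.

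Serious AEs and AEs of Grade 3 or higher are listed among the other secondary endpoints (Master Protocol Table 1). The IDMC reviews safety outputs about every 4 weeks (Master SAP 4.1). Section 8.4.4 requires every SAE to be notified within 24 hours whatever its cause, and a site that follows the Appendix 4 examples would not start that clock for a progression death. At stake are the completeness of these safety outputs and their consistency between sites.

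**Working it through.** The plan states no figure to reproduce here. The check sets the texts side by side; the arithmetic shows scale only.

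**Step 1: do the two rules conflict?** Take a patient who dies of COVID-19 progression after randomization.
- Appendix 4, Definition of SAE: death from progression is an example of an event that meets a seriousness condition yet cannot be an SAE, because it is taken not to be an AE.
- Section 8.4.7: progression is to be reported as an AE or SAE, as appropriate.

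The same event gets two answers.

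**Step 2: does the AE definition support the Appendix 4 examples?** No. It counts exacerbated disease and makes no exception for the disease under study. The list of non-AEs removes only fluctuations that do not worsen, and a fatal progression has worsened. Appendix 4 also says that clinical sequelae of lack of efficacy are reported if they meet the definition. Death is its first seriousness criterion, and it treats complications during a hospital stay as AEs. The examples are thus at odds with the rest of the appendix.

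**Step 3: does anything settle which text prevails?** Section 8.4 sends sites to Appendix 4 for the definitions, and Appendix 4 presents itself as the complete guidance. Section 8.4.7 is the more specific text, but its qualifier gives no criterion. No order of precedence is stated. The sub-protocols do not resolve it, and zilucoplan Section 4.1.2.1 adds a related mismatch: it leaves disease-associated laboratory findings out of the clinically significant class unless they are more severe than expected, whereas Section 8.4.7 includes them.

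**Step 4: which outputs depend on the answer?**
- Dependent, because they use AE or SAE recording: SAE and fatal-TEAE tables, the serious-TEAE risk difference, IDMC safety outputs, 24-hour notification.
- Not dependent, because deaths come from the Death Details page: Day 29 all-cause mortality (Master SAP 16.2.1.3) and the handling of deaths in the primary endpoint (16.1.1).

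**Step 5: scale.** Inputs from Master Protocol 9.1: 350 patients per arm, and assumed Day 29 mortality of 15% on placebo and 8.25% on a candidate agent.
- Placebo deaths: 350 × 0.15 = 52.5
- Agent deaths: 350 × 0.0825 = 28.9
- Per comparison: 52.5 + 28.9 = 81.4

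The documents do not give the share of deaths due to progression. Assuming 50% to 100%:
- 0.5 × 81.4 = 40.7, about 41
- 1.0 × 81.4 = 81.4, about 81

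Non-fatal serious worsening would come on top. The two terminated sub-protocols randomized far fewer patients: 29 for lanadelumab and 108 for zilucoplan (Section 16 of their SAPs). Even with 15% mortality throughout, that is 29 × 0.15 = 4.4 and 108 × 0.15 = 16.2 deaths.

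**The case against.** The best defense is that the Appendix 4 sentence is conditional. It creates no separate rule that COVID-19 deaths are not SAEs; the test is the AE definition, and under that definition worsening disease qualifies. Section 8.4.7 addresses this class of event directly, and Section 8.4.4 requires notification whatever the cause. On this view Appendix 4 agrees with Section 8.4.7 apart from one badly chosen example. The eCRF completion guidelines, which Appendix 2 mentions, may already settle the matter.

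The form of the sentence is conditional, and that stands. But the definition does not exclude the events named, so the examples make sense only as an exclusion of them, and an investigator will naturally read them that way. The guidelines are not among the documents, so they can be neither relied on nor faulted.

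A reader might infer more than the texts support:
- *That sites will record differently.* The documents show only that they can.
- *That SAE incidence could move by 15 percentage points.* This is an upper bound for the placebo arm. It needs every death to be from progression and no patient who died to have another recorded SAE, since each patient is counted once per category.
- *That about 26 deaths per arm would lack an SAE record.* This needs an even split of sites between the two texts, which has no source, and it applies the placebo rate to both arms. At 8.25% the same split gives about 14 in the agent arm.
- *That most serious events are disease-related, or that the safety figures become uninterpretable.* The documents say nothing about the first. Against the second, assignment is double-blind, Master SAP 17 plans no statistical comparison of safety data, and mortality is captured separately.

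**Conclusion.** The contradiction is real and unresolved. The examples in Appendix 4's SAE definition conflict with Section 8.4.7 and do not fit the AE definition in the same appendix. Sites can therefore differ on progression deaths and serious worsening, and the outputs listed as dependent in step 4 can be under-counted or site-dependent. With blinded assignment the expected effect is mainly noise and under-counting, not bias toward one arm.

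The range of about 41 to 81 deaths per comparison is an illustration. It rests on the plan's mortality assumptions, full enrollment of 350 per arm, and an assumed progression share of 50% to 100%. It counts deaths whose classification depends on the passage followed, not deaths expected to go unreported. The numbers are much smaller for the terminated sub-protocols. The point deserves correction because it concerns a stated rule and the remedy is cheap.

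**What to change.** Reconcile Section 8.4.7 with the AE and SAE definitions in Appendix 4 so that they give one reporting rule. Deleting the parenthetical from the opening sentence of the SAE definition would be one way: the conditional sentence would remain and would then agree with Section 8.4.7 and the AE definition. Check zilucoplan Section 4.1.2.1 against the same rule. Repeat the rule in the eCRF completion guidelines so that all sites and sub-protocols apply it alike.

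The cost is a one-line change in the next Master Protocol amendment, any matching edit to the zilucoplan text, and a memo to sites. The downside is possibly more SAE forms.
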